| ICH | International Conference on Harmonization |
| Kg | kilogram(s) |
| LC-MS | liquid chromatography–mass spectrometry |
| LLOQ | lower limit of quantitation |
| LLC | limited liability company |
| LOCF | Last observation carried forward |
| M | meter(s) |
| mCEQ | modified Cigarette Evaluation Questionnaire |
| MedDRA | Medical Dictionary for Regulatory Activities |
| Mg | milligram(s) |
| mITT | modified intent to treat |
| mL | milliliter(s) |
| MMRM | mixed model for repeated measures |
| N, n | sample size, number of observations |
| NBW | nicotine by weight |
| NE | nicotine Equivalents |
| Ng | Nanograms |
| NNAL | 4-(methylnitrosamino)-1-(3-pyridyl)-1-butanol |
| NNN | N-nitrosonornicotine |
| PFT | pulmonary function test |
| Pg | Pictogram |
| PMUSA | Phillip Morris USA |
| PP | per-protocol |
| Q1 | first quartile |
| Q3 | third quartile |

| | |
|---------|--|
| QGEN | Generic Quality of Life scales |
| RBC | red blood cell |
| SAE | serious adverse event |
| SAP | statistical analysis plan |
| SD | standard deviation |
| SEM | standard error of mean |
| sICAM-1 | soluble intercellular adhesion molecule-1 |
| SMS | short message service |
| TQOLIT | Tobacco-specific Quality of Life Impact Tool |
| WBC | white blood cell |
| WHO-DD | World Health Organization Drug Dictionary |

1. INTRODUCTION

The following Statistical Analysis Plan (SAP) provides the framework for the summarization of the data from this study. The analysis plan may change due to unforeseen circumstances. Any changes made after locking of the database will be documented in the Clinical Study Report (CSR).

Any additional analyses not addressed within this SAP and/or driven by the data, or requested by Altria Client Services LLC, will be considered out of scope and must be approved, by Altria Client Services LLC, and must be described in the CSR.

2. OBJECTIVES AND ENDPOINTS

2.1 Objectives

2.1.1 Primary Objective

The primary objective is to:

Compare absolute changes in selected biomarkers^a from Baseline^b to Week 24 (EOS) between adult smokers who continue to smoke conventional cigarettes (Control group) ad libitum and adult smokers who have completely^c switched to ad libitum use of test e-vapor products (Test groups) for 24 weeks.

^a Selected biomarkers include:

- o White Blood Cell Count (WBC Count)
- o High Density Lipoprotein Cholesterol (HDL-C)
- o Urinary 8-epi-prostaglandin F_{2α}
- o Urinary 11-Dehydrothromboxane B₂
- o Blood Soluble Intercellular Adhesion Molecule-1 (sICAM-1)
- o Urinary 4-(methylnitrosamino)-1-(3-pyridyl)-1-butanol and its glucuronides (total NNAL)
- o Carboxyhemoglobin (COHb)

^b Baseline of the 12-week ALCS-RA-16-06-EV study (CA20130), Week 1, will be used.

^c Subjects who exclusively use e-vapor products and have exhaled carbon monoxide (eCO) measurements ≤ 8 ppm from Week 6 (of the 12-week ALCS-RA-16-06-EV study) through Week 24 (EOS) and urine N-nitrosonornicotine (NNN) levels from

Week 6 (of the 12-week ALCS-RA-16-06-EV study) through Week 24 (EOS) consistent with switching to an e-vapor product.

2.1.2 Secondary Objectives

The secondary objectives are to:

- Assess changes in forced expiratory volume in the first second (FEV₁), forced vital capacity (FVC) and FEV₁/FVC ratios from Screening/Visit 2 of the 12-week ALCS-RA-16-06-EV study (CA20130) to Week 18 and to Week 24 (EOS) between the Test and Control groups.
- Compare changes in selected biomarkers (same as those in the primary objective) from Baseline to Week 18 between Test and Control groups.
- Determine the number of cigarettes smoked (Test and Control groups) from Baseline through Week 24 (EOS).
- Assess changes in the amount of test e-vapor product use (Test groups only) from Baseline through Week 24 (EOS).
- Assess adherence to protocol by comparing changes from Baseline through Week 24 (EOS) within the Test groups for eCO and urinary NNN.

2.1.3 Exploratory Objectives

The exploratory objectives are to:

- Assess changes in biomarkers of potential harm (BOPHs) and biomarkers of exposure (BOEs) (same as in the primary objective) from Baseline through Week 24 (EOS) between the subgroups that used different flavored Test e-vapor products.
- Assess changes in urine nicotine equivalents (NE) from Baseline through Week 24 (EOS) within and between Test and Control groups.
- Assess changes in the QGEN and TQOLIT questionnaires and the Cough Questionnaire responses from Baseline through Week 24 (EOS) between the Test and Control groups.
- Assess reasons for test product use/not-use at EOS and modified Cigarette Evaluation Questionnaire (mCEQ) questionnaires from Baseline to Week 24 (EOS) for the Test groups.
- Collect blood and urine samples for future assessment of BOE and or BOPH.

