2.2 Outcome Variables

Primary

The primary outcome variables are the absolute change from Baseline* Week 1 (Day 1) to Week 24 for each of the following primary biomarkers:

- whole blood WBC Count
- serum HDL-C
- creatinine-adjusted urine 8-epi-prostaglandin F_{2α}
- creatinine-adjusted urine 11-Dehydrothromboxane B₂
- serum sICAM1
- creatinine-adjusted urine total NNAL
- blood COHb saturation

*Baseline of the 12-week ALCS-RA-16-06-EV study (CA20130), Week 1, will be used.

Secondary

The secondary outcome variables are:

- Changes in FEV₁, FVC, and FEV₁/FVC ratios from Baseline to Week 18 and to Week 24 (EOS) in the Test and Control groups.
- The absolute change from Baseline to Week 18 for each of the primary biomarkers for each study group.
- The absolute change from Baseline to Week 24 for each of the primary biomarkers in the combined e-vapor use group (Test 1 + Test 2).
- Number of cigarettes smoked per day and test product used per day (number of new cartridges used and number of puffs taken, either ≤ 20 puffs or > 20 puffs) during Week 12 through week 24
- Frequency and percentage of subjects with a reduction, no change, or increase in cigarettes used per day from Baseline to Week 24
- Frequency and percentage of subjects with a reduction, no change, or increase in e-vapor cartridges used per day from Baseline to Week 24
- Creatine-adjusted urine NNN determined at Baseline, Week 18, and Week 24
- eCO determined at Baseline, Week 15, Week 18, Week 21, and Week 24

Exploratory

The exploratory outcome variables are:

- The differences between Baseline and Week 24 for the primary biomarkers in the Test groups.
- The creatinine-adjusted urine nicotine equivalent (NE) determined at Baseline, Week 18, and Week 24
- The absolute change in creatinine-adjusted urine NE from Baseline to Week 18 and from Baseline to Week 24
- Responses (Score) to the QGEN and TQOLIT questionnaires and the Cough Questionnaire recorded at Baseline, Week 18, and Week 24
- Responses to Reasons for Use and Not-use of Test Product at Week 24 (Test groups only) and mCEQ questionnaires from Baseline to Week 24

Clinical Safety

- AEs and SAEs
- Blood pressure, ECG, vital signs, clinical chemistry, urinalysis, and hematology

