6.1.5.2 Analysis Variables

- QGEN and TQOLIT questionnaires: responses, factor scores and the change in factor scores from Baseline* to Week 18 and Week 24
- Responses to each question on Cough Questionnaire at Baseline*, Visit 3 (Week 18) and Visit 5 (Week 24)
- Responses to Reasons for Use and Not-use of Test Product questionnaire at Visit 5 (Week 24) for test group only
- mCEQ: Response scores for each question, the factor scores for Smoking satisfaction, Psychological reward, Aversion, Enjoyment of sensation, and Craving reduction, and the change in factor scores from Baseline* to Week 24.

*Baseline values reported on Day 1 (Week 1) of the 12-week ALCS-RA-16-06-EV study (CA20130) will be used.

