6.2.6 Questionnaires

The responses and the following factor scores from the QGEN and TQOLIT will be presented and listed by subject and study visit:

- QGEN Physical Health General Score
- QGEN Emotional Health General Score
- QGEN estimated Physical Component Summary
- QGEN estimated Mental Component Summary
- TQOLIT Physical Functioning Supplemental
- TQOLIT General Health-Confidence
- TQOLIT Smoking Symptoms
- TQOLIT Smoking or Vaping Impact

The mCEQ will be considered as a 7-point scale and treated as a continuous variable. The responses from mCEQ-C or mCEQ-E will be listed as individual responses and as following factor scores¹ by subject and study visit:

- Smoking satisfaction: average of the response scores from questions 1, 2, and 12;
- Psychological reward: average of the response scores from questions 4 to 8;
- Aversion: average of the response scores from questions 9 and 10;
- Enjoyment of sensation: response score from question 3;
- Craving Reduction: response score from question 11.

Descriptive statistics (n, n missing, mean, SD, CV%, SEM, minimum, Q1, median, Q3, maximum, and 95% CI) of each of the response score and factor score will be provided by study group and study visit.

The responses from Cough Questionnaire (Baseline*, Visits 3 and 5) and Reasons of Use/Not-Use Test Product Questionnaire (Visit 5) will be listed by subject and study

¹ Cappelleri et al. 2007. Confirmatory factor analysis and reliability of the modified cigarette evaluation questionnaire. Addictive Behaviors. (32)912-923

visit. The frequency (n, %) of responses to Questions I and III through X will be summarized by study group. The responses to Question II will be summarized by study group using the same descriptive statistics as for the above questionnaires.

The above questionnaire analyses will be conducted using the dataset of subjects with a baseline and at least one post-baseline response for each individual question, with the exception of Reasons of Use/Not-Use, which will be summarized using available data.

*Baseline values reported on Day 1 (Week 1) of the 12-week ALCS-RA-16-06-EV study (CA20130) will be used.

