6.3.3 Exploratory Endpoint Analysis

The same statistical analysis model defined in the primary analysis Section 6.3.2 will also be used for the exploratory analysis to provide estimates for:

- Absolute changes in urine nicotine equivalents (NE) from Baseline to Week 18 and Week 24 between the each Test Group and the Control group and between the combined e-vapor use group (Test 1 + Test 2) and the Control group (mITT population).

For the following endpoints, the same statistical analysis model defined in the primary analysis Section 6.3.2 but without the fixed effect of BMI will be used for the exploratory analysis to evaluate:

- absolute changes in the QGEN and TQOLIT questionnaire responses from Baseline to Week 18 and Week 24 between the each Test Group and the Control group.

The following SAS codes will be used to perform the analysis:

```
Proc mixed data=<>;
Class subject gender group visit age;
Model response = gender group visit group*visit age baseline/ddfm=kr;
Repeated visit/type=<type> subject=subject;
LSmeans group*visit/CL alpha=0.05 pdiff;
Run;
```

For the endpoints with only Baseline and Week 24 measurements, an ANCOVA model will be used for the exploratory analysis to evaluate:

- absolute changes in the mCEQ factor score from Baseline to Week 24 in the Test and Control groups.

In the model, study group, gender, and age class (less than 45 years or greater or equal to 45 years) are the fixed effect factors. The baseline [Day 1 (Week 1) of the 12-week ALCS-RA-16-06-EV study (CA20130)] value of the measurement is the fixed effect covariate.

The following SAS codes will be used to perform the analysis:

```
proc mixed data=<>;
class subject gender group age;
model testname = gender group age baseline;
lsmeans group/diff cl alpha=0.05;
run;
```

Responses to the Reasons of Use/Not-Use Test Product questionnaire will be summarized using frequency count tables for each question.

Questionnaire analyses will be conducted using the dataset of subjects with a baseline and at least one post-baseline response for each individual question.

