Control Group = Continue smoking lit-end conventional cigarette

Program: /CAXXXX/ECR/sas_prg/pksas/PROGRAMNAME.sas DDMMMYYYY HH:MM

Programmer note: For mCEQ, only the Visit 5 comparison will be shown. The first footnote will be “The mixed model includes study group, gender, and age class as fixed effects, and baseline score as the covariate”.

QGEN, TQOLIT and mCEQ Questionnaire Statistical Comparison Tables 14.2.4.1.3.2, 14.2.4.2.3.2, and 14.2.4.3.4.2 will have the following format:

Table 14.2.4.1.3.2 Statistical Comparisons of Absolute Change From Baseline in <QGEN> Factor Scores Between Study Groups by Visit

Page 1 of X

| Subscale | Visit | Comparison | LS Means | | LS Mean Difference (Test - Reference) | XX% Confidence Intervals | p-Value |
|------------|-------|-------------------|----------|---------------|--|--------------------------|---------|
| | | | Test (n) | Reference (n) | | | |
| XXXXXXXXXX | 3 | Test 1 vs Control | X.XX (X) | X.XX (X) | XXX.XX | XX.XX - XXX.XX | X.XXXX |
| | | Test 2 vs Control | X.XX (X) | X.XX (X) | XXX.XX | XX.XX - XXX.XX | X.XXXX |
| | 5 | Test 1 vs Control | X.XX (X) | X.XX (X) | XXX.XX | XX.XX - XXX.XX | X.XXXX |
| | | Test 2 vs Control | X.XX (X) | X.XX (X) | XXX.XX | XX.XX - XXX.XX | X.XXXX |

<Same for the remaining subscales>

Note: The mixed model for repeated measures includes study group, study visit, study group by study visit interaction, gender, and age class as fixed effects, baseline score as the covariate, and subject as the random effect, with an < XX > variance-covariance matrix.

Least-squares means (LS Means) are calculated from the MMRM.

Test = First group in the comparison

Reference = Second group in the comparison

n = Number of observation used in the analysis

Baseline = Day 1 (week 1) of the 12-week ALCS-RA-16-06-EV study (CA20130)

Visit 3 = Week 18 (Day 126 ± 3)

Visit 5 = Week 24 (Day 168 ± 3)

Test 1 Group = e-Vapor Product XLCB

Test 2 Group = e-Vapor Product XLMB

Control Group = Continue smoking lit-end conventional cigarette

Program: /CAXXXX/ECR/sas_prg/pksas/PROGRAMNAME.sas DDMMYYYY HH:MM

Programmer note: For mCEQ, the model footnote will be “The mixed model includes study group, gender, and age class as fixed effects, and baseline score as the covariate. Least-squares means (LS Means) are calculated from the ANCOVA.”

Page 1 of X

Table 14.2.4.4.1 Summary of Cough Questionnaire Questions I and III through X by Study Group and Visit

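### The SAP's objective asks for change in cough responses between Test and Control, but only by-visit summaries are planned: no within-subject change and no Test–Control estimate with its precision

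*SAP*

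**What the plan says.** The exploratory objective in Section 2.1.3 names cough together with two other questionnaires: "Assess changes in the QGEN and TQOLIT questionnaires and the Cough Questionnaire responses from Baseline through Week 24 (EOS) between the Test and Control groups".

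Later sections treat the instruments differently.

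- **Outcome variable (2.2).** All three are listed as responses by visit: "Responses (Score) to the QGEN and TQOLIT questionnaires and the Cough Questionnaire recorded at Baseline, Week 18, and Week 24".
- **Analysis variable (6.1.5.2).** For two of them change is defined: "QGEN and TQOLIT questionnaires: responses, factor scores and the change in factor scores from Baseline* to Week 18 and Week 24". For cough the entry stops at responses to each question at Baseline, Visit 3 and Visit 5.
- **Summary (6.2.6).** "The frequency (n, %) of responses to Questions I and III through X will be summarized by study group". For the duration item, "The responses to Question II will be summarized by study group using the same descriptive statistics as for the above questionnaires".
- **Model (6.3.3).** A repeated-measures model by group is planned for two instruments: "absolute changes in the QGEN and TQOLIT questionnaire responses from Baseline to Week 18 and Week 24 between the each Test Group and the Control". An ANCOVA covers the mCEQ factor scores. Cough is not mentioned.
- **Outputs (8 and 10).** QGEN, TQOLIT and mCEQ each have a change table, a statistical summary and a statistical comparison. Cough has two tables, both by group and visit: "Table 14.2.4.4.1 Summary of Cough Questionnaire Questions I and III through X by Study Group and Visit" and its counterpart for Question II, 14.2.4.4.2.
- **Listing (Appendix 16.2.6.12.4.2).** Responses are listed by subject and visit, with no change column.

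**The concern.** The objective is about change from Baseline and about Test against Control. For cough, no planned variable, table or model expresses either. Two of the three instruments in one sentence get both; the third gets neither.

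This matters because cough can move in two directions when smokers switch to an inhaled e-vapor product: an existing cough may clear and a new one may start. Percentages at separate visits show only the balance. A small net fall could mean that a few coughs resolved and none began, or that many resolved while nearly as many began. A reader of the study report would want to tell these apart. The reader would also want to know how precisely the groups differ, which two sets of percentages do not show.

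**Working it through.** The SAP gives no cough rate, sample size or power for this endpoint, so there is no stated figure to reproduce. The check has two parts: a trace through the document, and a bound on what the planned table can reveal.

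**1. Trace**

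| Step | QGEN / TQOLIT | Cough |
|---|---|---|
| Objective (2.1.3) | change, Test vs Control | change, Test vs Control |
| Outcome variable (2.2) | responses by visit | responses by visit |
| Analysis variable (6.1.5.2) | responses, factor scores, change | responses by visit |
| Between-group model (6.3.3) | MMRM on change | none |
| Tables (8, 10) | by visit, change, LS means, comparison with CI | by visit only |

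The instruments part at the analysis variable and do not rejoin.

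**2. What by-visit counts leave open**

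Inputs: group sizes from Section 3 (Test 1 n = 50, Control n = 52). Cough counts are assumed for illustration, and the same subjects are assumed to answer at both visits.

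Let b and e be the numbers answering yes to Question I at Baseline and at the later visit.

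- New-onset count lies between max(0, e − b) and min(e, n − b).
- Resolved = new-onset + b − e.

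Test 1, b = 20 and e = 15: new-onset runs from 0 to min(15, 30) = 15, and resolved from 5 to 20.

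Test 1, b = 20 and e = 20: new-onset runs from 0 to 20, and resolved equals it. The table shows no change in either case.

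**3. Precision of a group difference in change**

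SE of one group's net change = sqrt[(new + resolved) − (new − resolved)²/n] / n.

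Take Test 1 going from 20/50 to 10/50 and Control from 21/52 to 21/52. Net change is −0.20 in Test 1 and 0 in Control, a difference of −20 points.

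- Fewest transitions: Test 1 has 0 new and 10 resolved, SE = sqrt(10 − 2)/50 = 0.057. Control has none, SE = 0. Combined SE 0.057; 95% CI −31 to −9 points.
- Most transitions: Test 1 has 10 new and 20 resolved, SE = sqrt(30 − 2)/50 = 0.106. Control has 21 new and 21 resolved, SE = sqrt(42)/52 = 0.125. Combined SE = sqrt(0.106² + 0.125²) = 0.164; 95% CI −52 to +12 points.

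The same printed table is compatible with an interval that excludes zero and with one that does not. These are outer limits; real data would fall between them.

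**The case against.** The strongest reply is that describing a mostly categorical exploratory questionnaire is a legitimate choice and that the SAP makes it consistently for cough from Section 2.2 to the shells. Section 3 calls the analysis mostly exploratory. The objective says *assess*, whereas the primary objective says *compare*. The verb settles little, however. Section 2.1.2 also says *assess* for lung function, and Section 6.3.2 models that by group. QGEN and TQOLIT sit under the same verb in the same sentence and are modelled too. It does mean that a p-value is not required.

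A reader might infer that no group difference in change can be seen at all, or that a new-cough signal would go unnoticed. The documents do not support that:

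- The shell of Table 14.2.4.4.1 sets Baseline, Visit 3 and Visit 5 side by side, and its programmer note adds Control at each visit. Net change per group, and the difference between groups, can be read off. The reading is approximate, because a subject needs only a Baseline and one later response to be included.
- Section 7.2 summarises use-emergent adverse events by group and system organ class, and the TQOLIT Smoking Symptoms score is modelled. Both are partial safeguards: the SAP does not say that a questionnaire cough becomes an adverse event, and the TQOLIT items are not shown.
- Subject-level responses are listed, so transitions could be worked out by hand.

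It is also fair that the objective does not name individual transitions and that mean change in the other scores hides them too. Those scores do, however, get a change estimate with an interval. Finally, the absence of a pooled Test column is no gap specific to cough: the other questionnaire shells have none either.

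**Conclusion.** The mismatch holds. Section 2.1.3 asks for change in cough responses between Test and Control, and the plan delivers by-visit frequencies, with descriptive statistics for Question II. Net change is approximately readable; within-subject change and a Test–Control estimate with its precision are missing, although the other two instruments in the objective have a change estimate and an interval.

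The size is modest. One exploratory objective is only partly answered, and no primary or secondary analysis is touched. The illustration (0 to 15 new coughs behind one table; a standard error anywhere from 0.057 to 0.164) rests on assumed cough counts and complete pairs, and shows what the table leaves open rather than what will happen.

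**What to change.** In Sections 6.1.5.2, 6.2.6 and 6.3.3, and in the table list and shells:

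1. **Question I, shift tables.** Baseline-by-Week 18 and Baseline-by-Week 24, by Test 1, Test 2 and Control, showing cough at neither visit, resolved, new-onset and persistent.
2. **Question I, group estimate.** An exploratory estimate with 95% CI of each Test–Control difference at Week 24, from a logistic model with group, Baseline response, gender and age class. The covariates match those in the QGEN and TQOLIT model. State the scale of the estimate, and say that only counts will be shown if cells are too sparse for the model.
3. **Items V, IX and X.** Counts improved, unchanged and worsened from Baseline. The SAP already does this for product use, with reduction, no change and increase (Section 6.2.5, Table 14.2.2.2). Full transition tables would be too sparse: item V has 5 levels and items IX and X have 7, so 25 or 49 cells for about 50 subjects per group. Define direction per item, because a higher code means more cough symptoms on V and fewer on IX and X.

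The data are already collected at Baseline, Visit 3 and Visit 5. The cost is SAP wording and a few extra tables. The estimates will be imprecise and should be labelled exploratory. If the sponsor prefers to keep cough descriptive, the minimum is to reword Section 2.1.3 so that it promises only a by-visit description.

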2.2 Outcome Variables

Primary

The primary outcome variables are the absolute change from Baseline* Week 1 (Day 1) to Week 24 for each of the following primary biomarkers:

- whole blood WBC Count
- serum HDL-C
- creatinine-adjusted urine 8-epi-prostaglandin F_{2α}
- creatinine-adjusted urine 11-Dehydrothromboxane B₂
- serum sICAM1
- creatinine-adjusted urine total NNAL
- blood COHb saturation

*Baseline of the 12-week ALCS-RA-16-06-EV study (CA20130), Week 1, will be used.

Secondary

The secondary outcome variables are:

- Changes in FEV₁, FVC, and FEV₁/FVC ratios from Baseline to Week 18 and to Week 24 (EOS) in the Test and Control groups.
- The absolute change from Baseline to Week 18 for each of the primary biomarkers for each study group.
- The absolute change from Baseline to Week 24 for each of the primary biomarkers in the combined e-vapor use group (Test 1 + Test 2).
- Number of cigarettes smoked per day and test product used per day (number of new cartridges used and number of puffs taken, either ≤ 20 puffs or > 20 puffs) during Week 12 through week 24
- Frequency and percentage of subjects with a reduction, no change, or increase in cigarettes used per day from Baseline to Week 24
- Frequency and percentage of subjects with a reduction, no change, or increase in e-vapor cartridges used per day from Baseline to Week 24
- Creatine-adjusted urine NNN determined at Baseline, Week 18, and Week 24
- eCO determined at Baseline, Week 15, Week 18, Week 21, and Week 24

Exploratory

The exploratory outcome variables are:

- The differences between Baseline and Week 24 for the primary biomarkers in the Test groups.
- The creatinine-adjusted urine nicotine equivalent (NE) determined at Baseline, Week 18, and Week 24
- The absolute change in creatinine-adjusted urine NE from Baseline to Week 18 and from Baseline to Week 24
- Responses (Score) to the QGEN and TQOLIT questionnaires and the Cough Questionnaire recorded at Baseline, Week 18, and Week 24
- Responses to Reasons for Use and Not-use of Test Product at Week 24 (Test groups only) and mCEQ questionnaires from Baseline to Week 24

Clinical Safety

- AEs and SAEs
- Blood pressure, ECG, vital signs, clinical chemistry, urinalysis, and hematology

